6.4. Windows for Analysis Time Points

Data analyzed by-visit-analysis will be summarized by the scheduled visit described in protocol section 9.1 Schedule of Events. Below are the definitions for the visit windows programmatically imposed on all available measures from unscheduled visits collected over the course of the study including early termination visit and end of study visit. No analysis visit windows will be applied for the study scheduled visits nor for drug concentration and immunogenicity data.

The visit windows are constructed using ranges applied to the number of days in study (study days) when the measure is collected. Below are the relevant definitions for the analysis visit windows:

1. The first study treatment occurs on Study Day 1.
2. Study day is defined as the number of days since the first study treatment administration+1.
3. Since the protocol specifies that measurements be collected before study treatment is administered on a given day, it is appropriate that baseline include Day 1.
4. For randomized but not treated subjects, Day 1 is the day of randomization.

Table 4: Efficacy Analysis Windows for Unscheduled Visits with RT-qPCR or Viral Load Results

Visit Label	Targeted Study Day	Analysis Window in Study Day
Baseline	1	≤ 1
Week 1	8	[2, 11]
Week 2	15	[12, 18]
Week 3	22	[19, 25]
Week 4	29	[26, 32]
Week 5	36	[33, 39]
Week 6	43	[40, 46]
...
Week x	$29+7x$	$[26+7(x-4), 32+7(x-4)]$

If a subject has multiple efficacy assessment visits within an analysis visit window, the one with worst result (e.g., the positive test result will be used for analysis if one record is positive and the other one is negative; the highest viral load result will be used if multiple viral load results are in the same analysis window.) will be selected. If the test results are all negative, the value of the latter visit will be used. If there are multiple positive RT-qPCR results within an analysis window, the record with the highest quantitative result will be used.

Table 5: Global Analysis Windows for Data Other Than RT-qPCR Test

Visit Label	Targeted Study Day	Analysis Window in Study Day
Baseline	1	≤ 1
Day 2	2	[2, 2]
Day 4	4	[3, 4]
Week 1	8	[5, 11]
Week 2	15	[12, 18]
Week 3	22	[19, 25]
Week 4	29	[26, 42]
Week 8	57	[43, 70]
Week 12	85	[71, 98]
Week 16	113	[99, 126]
Week 20	141	[127, 154]
Week 24	169	[155, 182]
Week 28	197	[183, 210]
Week 32	225	≥ 211

Unscheduled Assessments

For efficacy, safety laboratory data, and vital signs, unscheduled visit measurements may be used to provide a measurement for a time point, including baseline, if appropriate according to their definitions. The measurements may also be used to determine abnormal values, AESIs, and PCSVs.

6.5. Pooling of Centers for Statistical Analyses

Currently, the randomization is stratified by site. Since a potential differential treatment effect among countries may exist, region variable as a fixed effect factor will be included in the statistical analysis model. A subgroup analysis regarding region will also be performed for the primary efficacy endpoint. Results will also be summarized descriptively by country.

6.6. Statistical Technical Issues

To consider the potential impact that not all of study subjects come from a household with more than one member participating this trial, a simulation has been conducted to explore the potential impact to the type I error rate and power by the percent of households with a single study subject only.

This simulation is based on the same sample size of 1248 (See [Table 1](#) in Section 2.2.1) assuming the attack rates are 10% and 5% in placebo and REGN10933+REGN10987 treatment group, respectively. The correlated Bernoulli response data (e.g. 1=infected vs 0=not infected) within a household was generated by using Gaussian multivariate cumulative distribution function proposed by Emrich and Piedmonte (1991). For example, the table below exhibits the correlation between the bivariate normal data with correlation ρ used to generate the Bernoulli correlated data and the corresponding Bernoulli correlation γ in the cases where the attack rates are both 10% (e.g., $p_1 = p_2 = 0.1$ under the null hypothesis), and 10% and 5% (e.g., $p_1 = 0.1, p_2 = 0.05$ under the alternative hypothesis).

$p_1 = p_2 = 0.1$		$p_1 = 0.1, p_2 = 0.05$	
ρ Normal	γ Bernoulli	ρ Normal	γ Bernoulli
0.1	0.03706	0.1	0.03065
0.2	0.07996	0.2	0.06748
0.3	0.12907	0.3	0.11089
0.4	0.18504	0.4	0.16150
0.5	0.24891	0.5	0.22020
0.6	0.32242	0.6	0.28834
0.7	0.40866	0.7	0.36813
0.8	0.51381	0.8	0.46328
0.9	0.65405	0.9	0.58016

Given the percent of subjects from households with single study subject (HHS), the rest of household size was randomly generated by using a truncated Poisson ($l = 4$) (i.e., resampling if ≤ 1). The simulation is repeatedly 2000 times by different HHS to compare the power between GEE model and logistic regression model based on boundary p-value=0.044 after 2 planned interim analyses.

Summary of power and type I error rate between the GEE model and logistic regression model by different HHS, considering the extreme high correlated data. The power is based on the testing p-value compared to the boundary p-value of 0.044 after 2 interim analyses at 50% and 75% information fraction for the final analysis.

Comparisons of Power

$\gamma = 0.58 (p_1 = 0.1, p_2 = 0.05)$		
HHS(%)	power-GEE	power-Logistic
10	0.9920	0.9035
20	0.9905	0.9040
30	0.9855	0.9140

Comparisons of Type I Error

$\gamma = 0.65 (p_1 = 0.1, p_2 = 0.1)$		
HHS(%)	α -GEE	α -Logistic
10	0.0480	0.0435
20	0.0490	0.0440
30	0.0495	0.0475

40	0.9590	0.8980
50	0.9245	0.9075
60	0.9035	0.9085
70	0.8640	0.9175
80	0.8460	0.9155

40	0.0510	0.0445
50	0.0410	0.0360
60	0.0600	0.0490
70	0.0575	0.0390
80	0.0735	0.0370

Based on the potential inflation of type I error (α) and decreasing power as HHS over 50%, conservatively the percent of households with a single study subject could be higher than 70%. Thus, if this situation occurs, the logistic regression will be used instead of using GEE approach.

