## 6.2. Planned Interim Analysis

There is no interim analysis planned after the administrative assessment.

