2.2. Sample Size and Power Considerations

2.2.1. Cohort A

The primary hypothesis is the reduction in the proportion of symptomatic RT-qPCR (broad-term) confirmed SARS-CoV-2 infections in seronegative subjects. To calculate the sample size to achieve at least 90% power for seronegative subjects in cohort A, it is assumed that the statistical hypothesis will be tested in a 2-sided test. Based on the administrative assessment results among 409 seronegative subjects in cohort A, an approximately 50% reduction of infection (symptomatic or asymptomatic) compared to placebo group and a 100% reduction of symptomatic infection compared to placebo group was observed. Due to the small sample size in the administrative assessment, it was assumed, for the purpose of assessing study power, that an approximately 50% reduction or greater in symptomatic infections compared to the placebo group will be expected for the final primary efficacy analysis.

In this household study design, the number of subjects per household, the correlation between subjects and symptomatic infection rates within a household are unknown. To detect a relative risk of 0.5 (i.e., 50% reduction of the assumed 10% attack rate in the placebo arm), equivalent to an odds ratio of 0.47, power was calculated compared to the p-value of 0.05 based on 2000

simulations in 1248 subjects from 430 households (i.e., assuming an average household size of 2.9 seronegative subjects). **Table 1** provides power calculations by varying degrees of correlation within household. In all cases, the power of the study is >90% using a generalized linear model with the generalized estimation equation (GEE) approach assuming a compound symmetry covariance matrix.

Table 1: Simulated Power for Household Design (1248 Subjects over 430 Households)

Placebo Attack Rate	REGN10933+ REGN10987 Attack Rate	Correlation within Household	Average Odds Ratio REGN10933+REGN10987 versus Placebo	Power
10%	5%	0.1	0.485	0.914
10%	5%	0.2	0.485	0.934
10%	5%	0.3	0.480	0.956
10%	5%	0.4	0.481	0.972
10%	5%	0.5	0.476	0.983
10%	5%	0.6	0.478	0.999

At least 1980 subjects will need to be enrolled in cohort A to have a minimum of 1248 seronegative subjects, assuming that 10% of subjects drop out, and 30% of subjects are seropositive at baseline.

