5.7.2. Adjustment for Multiple Comparison

The overall type I error will be controlled in each of seronegative mFAS-A and seronegative mFAS-B independently at 2-sided 5% significance level.

Seronegative mFAS-A Subjects

The overall type I error will be controlled for the primary hypothesis in Cohort A based on a 2-sided test at an alpha level of 0.05 as follows:

H0: There is no treatment difference between REGN10933+REGN10987 and placebo in the proportion of subjects with a symptomatic RT-qPCR confirmed SARS-CoV-2 infection during the EAP.

H1: There is a treatment difference between REGN10933+REGN10987 and placebo in the proportion of subjects with a symptomatic RT-qPCR confirmed SARS-CoV-2 infection during the EAP

If the primary efficacy endpoint in Cohort A is statistically significant, the alpha level of 0.05 will be released for the key secondary endpoints in Cohort A. The hierarchy testing sequence of key secondary endpoints is presented in the following table.

Table 2: Hierarchy Testing Sequence of Key Secondary Efficacy Endpoints in Seronegative mFAS-A

Key Secondary Efficacy Variables
Proportion of subjects with viral load >4 (log10 copies/mL) in NP swab samples during the EAP
Number of weeks of symptomatic RT-qPCR confirmed SARS-CoV-2 infection (broad-term) during the EAP
Number of weeks of high-viral load >4 (log10 copies/mL) in NP swab samples during the EAP
Number of weeks of RT-qPCR confirmed SARS-CoV-2 infection (regardless of symptoms) during the EAP
Proportion of subjects who have a RT-qPCR confirmed SARS-CoV-2 infection (regardless of symptoms) during the EAP
Proportion of subjects in placebo group with a RT-qPCR confirmed SARS-CoV-2 infection during the EAP with an index case participating in study R10933-10987-COV-2067 (comparison of those whose index cases receive REGN10933+REGN10987 vs placebo in R10933-10987-COV-2067)

Seronegative mFAS-B Subjects

The overall type I error will be controlled for the primary hypothesis in Cohort B based on a 2-sided test at an alpha level of 0.05 as follows:

H0: There is no treatment difference between REGN10933+REGN10987 and placebo in the proportion of subjects who subsequently develop signs and symptoms (broad-term) within 14 days of a positive RT-qPCR at baseline or during the EAP

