5.7.5. Interim Analysis

No interim analysis will be conducted for this study.

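### The SAP 6.6 tables behind the GEE-to-logistic switch rule use a 0.044 boundary after two interim analyses, but the planned cohort A test is a single 2-sided 0.05 test

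*SAP*

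**What the plan says.** SAP 6.6 describes 2000 simulated trials at each level of HHS, the share of subjects who are alone in their household within the study. Attack rates are 10% and 5%, the within-household correlation is extreme, and "This simulation is based on the same sample size of 1248". The section gives the cut-off twice: "boundary p-value=0.044 after 2 planned interim analyses" and, for the power figures, "boundary p-value of 0.044 after 2 interim analyses at 50% and 75% information fraction for the final analysis".

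The rest of the plan describes a different design:

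- SAP 5.7.5: "No interim analysis will be conducted for this study". Protocol 11.5 says the same.
- Protocol 6.2: "There is no interim analysis planned after the administrative assessment".
- SAP 5.7.2 controls the cohort A primary hypothesis with a "2-sided test at an alpha level of 0.05".
- SAP 2.2.1, for the same 1248 subjects: "power was calculated compared to the p-value of 0.05".

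SAP 5.7.1 and Protocol 11.4.3.1 both rest the 70% switch from GEE to logistic regression on these simulations.

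**The concern.** The switch rule decides which model produces the primary p-value, and SAP 6.6 is its only documented support. If that section was computed at a nominal level the trial will not use, its power and type I error are not those of the planned test.

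The type I table carries no statement of its nominal level. A reader who knows the primary test is at 0.05 will naturally judge the column against 0.05. At the threshold this changes the reading: the GEE value at 70% HHS looks compatible with 0.05 but is clearly above 0.044.

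**Working it through.** **1. Reproduce the stated logistic power.** Inputs from SAP 6.6 and 2.1: 1248 subjects at 1:1, so 624 per arm, with rates 0.10 and 0.05. Normal approximation with pooled null variance:

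- Null SE = sqrt(2 × 0.075 × 0.925 / 624) = 0.01491
- Alternative SE = sqrt((0.09 + 0.0475) / 624) = 0.01484
- At 0.044: (0.05 − 2.014 × 0.01491) / 0.01484 = 1.345, power 0.9107
- At 0.05: (0.05 − 1.960 × 0.01491) / 0.01484 = 1.399, power 0.9192

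The SAP logistic column runs from 0.8980 to 0.9175, in line with 0.9107. Moving to 0.05 adds 0.9192 − 0.9107 = 0.0085, or about 0.8 points.

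**2. Which level was used for the type I table?** The text ties 0.044 explicitly to power only, so this must be inferred. The eight logistic values (0.0435, 0.0440, 0.0475, 0.0445, 0.0360, 0.0490, 0.0390, 0.0370) average 0.0426 over 8 × 2000 = 16,000 null replicates.

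- Against 0.044: SE = sqrt(0.044 × 0.956 / 16,000) = 0.00162, z = −0.9
- Against 0.05: SE = sqrt(0.05 × 0.95 / 16,000) = 0.00172, z = −4.3

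The column fits 0.044 and not 0.05.

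**3. Re-simulation at both levels.** Settings: Gaussian copula with normal correlation 0.9, individual 1:1 randomization, singles as the stated percent of subjects, other households Poisson(4) resampled if 1 or fewer, unadjusted logistic and exchangeable GEE with robust SE, 10,000 replicates per HHS level. The induced binary correlations are 0.6541 and 0.5802, matching the SAP's 0.65405 and 0.58016.

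| Quantity, HHS 10–80% | at 0.044 | at 0.05 |
|---|---|---|
| Logistic power | 0.904–0.911 | 0.912–0.920 |
| Logistic type I error | 0.041–0.048 | 0.047–0.054 |

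Logistic type I error averages 0.0441 at 0.044 and 0.0500 at 0.05, a rise of about 0.6 points. Because the logistic test holds its nominal level here, its column is a fair gauge of the level used, which supports step 2. Among converged GEE fits, power rises by 0.1 to 0.8 points and type I error by 0.5 to 0.8 points.

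**4. The SAP's GEE type I column against each level.** With 2000 replicates, SE = sqrt(0.044 × 0.956 / 2000) = 0.0046 at 0.044, and sqrt(0.05 × 0.95 / 2000) = 0.0049 at 0.05.

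| HHS % | GEE type I (SAP) | z vs 0.044 | z vs 0.05 |
|---|---|---|---|
| 10 | 0.0480 | 0.9 | −0.4 |
| 20 | 0.0490 | 1.1 | −0.2 |
| 30 | 0.0495 | 1.2 | −0.1 |
| 40 | 0.0510 | 1.5 | 0.2 |
| 50 | 0.0410 | −0.7 | −1.8 |
| 60 | 0.0600 | 3.5 | 2.1 |
| 70 | 0.0575 | 2.9 | 1.5 |
| 80 | 0.0735 | 6.4 | 4.8 |

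**5. Does the boundary alone change the model comparison?** No. In the SAP, logistic power exceeds GEE power from 60% HHS upward (0.9085 against 0.9035 at 60%; 0.9175 against 0.8640 at 70%). With non-converged GEE fits counted as non-significant, the re-simulation at 70% gives 0.9111 (logistic) against 0.8514 (GEE) at 0.044, and 0.9200 against 0.8575 at 0.05. The ordering is the same at both levels.

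**The case against.** The strongest reply is that SAP 6.6 is a relative comparison of two models at one common cut-off, under deliberately extreme correlation, and is not the trial's power statement. That statement, SAP Table 1 and Protocol Table 9, is already at 0.05. No decision is shown to change, since logistic power stays above 90% and the ordering at high HHS does not reverse. All of this stands, and it keeps the point small. It does not make the 6.6 tables correct for the planned test.

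Protocol 6.3.1 still says the monitoring committee may be asked for a formal interim efficacy evaluation. It points to Section 11.5 for this, and that section says there will be none, so it does not rescue the 0.044 boundary.

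Four stronger readings are tempting, and the documents do not support them:

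- *GEE type I error is above target throughout.* At 10% to 40% the values are only 0.9 to 1.5 SE above 0.044, and the 50% value lies below it. The five values from 10% to 50% average 0.0477, which is 1.8 SE above 0.044 over 10,000 replicates.
- *The SAP misread the inflation when it set the threshold.* SAP 6.6 does not compare the column with 0.05. It notes possible inflation and falling power above 50% HHS, and acts on both.
- *The 0.05 values follow by multiplying the GEE column by 0.05/0.044.* Inflation that comes from estimator behaviour need not scale in proportion. The re-simulation also did not reproduce the GEE inflation at 60% to 80% (0.043 to 0.046 at 0.044 among converged fits). The SAP does not say how non-converged fits were handled, so this does not show its figures to be wrong.
- *The 70% threshold is wrong.* The boundary error alone does not show that.

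**Conclusion.** The point holds as a limited one. SAP 6.6 reports power, and by inference type I error, for a three-look design that the trial no longer has, and these tables are the stated basis of the primary-model switch rule. For the planned test, logistic power is understated by about 0.8 points and logistic type I error by about 0.6 points. GEE type I error is clearly above the level used at 60%, 70% and 80% HHS, and compatible with it at each level from 10% to 50%.

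This rests on two things. The 0.044 level for the type I table is inferred from the logistic column rather than stated. The re-simulation used unadjusted models, because the SAP does not say which covariates were simulated. It matched the stated GEE power within 2 points at 10% to 70% HHS only when non-converged fits counted as non-significant; at 80% it gave 0.78 against 0.846.

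**What to change.** Before the first-step database lock:

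- Re-run the 6.6 simulation at 2-sided 0.05 with no interim looks, and replace both tables.
- Delete the two references to interim analyses and the 0.044 boundary.
- State the nominal level beside the type I table, and say how non-converged GEE fits are counted.
- Define HHS as a percentage of households, the unit of the rule in SAP 5.7.1, then confirm or restate the 70% threshold from the new tables. The unit matters. Poisson(4) restricted to 2 or more has mean 4 × (1 − e⁻⁴) / (1 − 5e⁻⁴) = 4.32, so 70% of subjects corresponds to 0.70 / (0.70 + 0.30/4.32) = 91% of households.

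The cost is a re-run of an existing program and an edit to one SAP section. If the threshold moves, SAP 5.7.1, Protocol 11.4.3.1 and the protocol synopsis need the same number. No new data and no change to enrolment or sample size are required.

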7. TIMING OF STATISTICAL ANALYSES

There are multiple steps of analyses planned for this study.

- An administrative descriptive analysis based on approximately first 554 randomized Cohort A subjects has been conducted. No formal statistical hypothesis testing will be performed. The individuals who have the subject treatment information will be described in the communication plan.
- The first step analysis: The database lock will occur when all Cohort A and Cohort B subjects complete the EAP and all their data during the EAP have been collected and validated. The individual treatment codes will be unblinded and final analyses of the primary and some secondary efficacy endpoints of cohort A and Cohort B will be conducted. The subjects who are included in the administrative analysis will not be included in the first step efficacy analysis. Also, subjects who are randomized after January 28th (approximately 269) will not be included in this analysis.

Note: The results of primary and some secondary efficacy endpoints in the first step analysis maybe used for a submission dossier to health authorities.

- The second step analysis (final analysis): The database lock will occur after the last subject completes the study. All treated subjects including 554 subjects in the administrative assessment, subjects in the first step analysis, and those subjects (~269) who were randomized after 28 January, 2021, will be included in the safety analysis. The second-step analysis for efficacy will include all subjects except those subjects who were included in the administrative assessment.

8. SOFTWARE

All analyses will be done using SAS Version 9.4 or higher, and R 3.5.3 or higher.

10. APPENDIX

10.1. Summary of Statistical Analyses

Primary Efficacy Analysis:

Endpoint	Analysis Population	Estimand	Statistical Method	Supportive Analysis	Subgroup Analysis	Other Analyses
Proportion of subjects who have a symptomatic RT-qPCR confirmed SARS-CoV-2 infection (broad-term) during the EAP	Seronegative mFAS-A	A broad-term symptom occurring within a 14-days window of any positive RT-qPCR during the EAP regardless of adherence to study treatment will be included for the primary analysis.	A generalized linear model with the generalized estimation equation (GEE) approach or logistic regression. If percent of households with single study subject greater than or equal to 70%. Missing RT-qPCR will be imputed as positive RT-qPCR if a subject with COVID-19 signs and symptoms (broad-term) occurring within a 14-day window of a visit with missing RT-qPCR data.	Yes	Yes	
 1. Excluding those subjects who develop asymptomatic or symptomatic SARS-CoV-2 infection within 72 hours of the study drug administration 2. Exclude subjects from non-GCP compliance sites
Proportion of subjects who have a symptomatic RT-qPCR confirmed SARS-CoV-2 infection (broad-term) at baseline or during the EAP	Seronegative mFAS-B	Same as above including a positive RT-qPCR at baseline	Same as above including a positive RT-qPCR at baseline	Yes	No	
 1. Exclude subjects from non-GCP compliance sites

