**Primary Efficacy Analysis (Cohort A)**

The primary efficacy endpoint will be analyzed in the seronegative mFAS-A population. In order to account for the correlation among subjects within a household and control the associated type 1 error inflation, a generalized linear model will be used to estimate the odds ratio between the treatment groups by using the GEE approach. This model estimates a single within-household correlation coefficient. The model will include the fixed category effects of treatment group (placebo versus REGN10933+REGN10987), region (US vs ex-US), and age ( $\geq 12$  to  $< 50$ ,  $\geq 50$  years). The model will use a compound symmetry covariance matrix and estimate the odds ratio between the treatment groups and corresponding 95% CI and p-value. If the GEE model fails to converge due to most households containing only a single study subject in

---

seronegative mFAS-A or the percentage of households with only a single study subject is 70% or more, then a logistic regression model will be used, with treatment, region, and age group as fixed effects.

Subjects with COVID-19 symptoms that are missing a central lab determined RT-qPCR test during the EAP (eg. are too sick to go to the study site) but have a positive SARS-COV-2 test from a local lab (eg. in the hospital) will be considered as having a symptomatic infection if any of the symptoms occurred within 14 days of the positive SARS-COV-2 test.

Additional sensitivity analyses for missing data are described in the protocol.

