### **Cohort B**

The cohort B primary efficacy endpoint described in Section 4.2.1 will be analyzed in the seronegative mFAS-B population (Section 11.3.1). The same statistical methods as described for cohort A will be used to obtain the estimate of odds ratio and p-value for comparison between the treatment groups.

In cohort B, a subject will be considered having a symptomatic RT-qPCR confirmed SARS-CoV-2 infection (broad-term) during the EAP if subjects have at least 1 symptom within 14 days of a positive RT-qPCR result at baseline or during the EAP.

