### **Handling of Missing Central Lab SAR-CoV-2 RT-qPCR Data for Both Cohort A and Cohort B**

Subjects with COVID-19 symptoms that are missing a central lab-determined RT-qPCR test during the EAP (eg, are too sick to go to the study site) but have a positive SARS-CoV-2 test from a local lab (eg, in the hospital) will be considered as having a symptomatic infection if any of the symptoms occurred within 14 days of the positive SARS-CoV-2 test(s).

The graphical display using Kaplan-Meier curve for the time to first symptom will also be provided.

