1.2.4. Modifications from the Statistical Section in the Final Protocol

There are no modifications compared to protocol amendment 6.

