In Cohort B, a subject will be considered having a symptomatic RT-qPCR confirmed SARS-CoV-2 infection (broad-term) during the EAP if subjects have at least one symptom within 14 days of a positive RT-qPCR result at baseline or during the EAP.

Handling of Missing Central Lab SAR-CoV-2 RT-qPCR Data for Both Cohort A and Cohort B

Subjects with COVID-19 symptoms that are missing a central lab determined RT-qPCR test during the EAP (eg. are too sick to go to the study site) but have a positive SARS-CoV-2 test from a local lab (eg. in the hospital) will be considered as having a symptomatic infection if any of the symptoms occurred within 14 days of the positive SARS-CoV-2 test that was observed during the EAP.

The graphical display using Kaplan-Meier curve for the time to first symptom will also be provided.

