6.2. Data Handling Convention for Efficacy Variables

Rules for handling missing RT-qPCR test results for primary and secondary efficacy variables are described in Section [5.7.1](#).

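### SAP 10.1 imputes a missing RT-qPCR as positive from symptoms alone, contradicting the positive-local-test rule in SAP 5.7.1, protocol 11.4.3.1 and the synopsis

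*SAP*

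**What the plan says.** SAP 10.1, Statistical Method column, first primary row (cohort A): "Missing RT-qPCR will be imputed as positive RT-qPCR if a subject with COVID-19 signs and symptoms (broad-term) occurring within a 14-day window". The sentence ends by tying that window to the visit with no result. It mentions no local test. The cohort B row takes over the same method by reference and adds the positive RT-qPCR at baseline.

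SAP 5.7.1, for both cohorts, deals with symptomatic subjects who lack a central RT-qPCR result. Those who lack one "but have a positive SARS-CoV-2 test from a local lab (eg. in the hospital) will be considered as having a symptomatic infection", provided that a symptom fell "within 14 days of the positive SARS-CoV-2 test that was observed during the EAP". Protocol 11.4.3.1 has the same rule ("but have a positive SARS-CoV-2 test from a local lab (eg, in the hospital) will be considered as having a symptomatic infection"), and so does the synopsis for cohort A ("but have a positive SARS-COV-2 test from a local lab (eg. in the hospital) will be considered as having a symptomatic infection"). Neither protocol text says that the local test must fall within the efficacy assessment period (EAP).

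Two further SAP statements bear on which text is right. SAP 6.2 says: "Rules for handling missing RT-qPCR test results for primary and secondary efficacy variables are described in Section" 5.7.1. SAP 1.2.4 says: "There are no modifications compared to protocol amendment 6".

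**The concern.** The two rules use different evidence and different anchors. SAP 10.1 needs only a symptom near a missed swab. SAP 5.7.1 needs a positive test and a symptom near that test. A subject with a runny nose near a missed weekly swab, and no test at all, is a primary event under 10.1 and not under 5.7.1. The broad-term list in SAP 4.5 is long: it includes headache, sneezing and an open category for other symptoms.

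SAP 10.1 is the compact statement of the primary analysis and could be programmed from directly. It would then put events with no positive test into an endpoint defined as RT-qPCR confirmed. False events of this kind, if equally frequent in both arms, dilute the cohort A treatment effect. In cohort B there is less room for a difference, because every subject in the seronegative mFAS-B is already positive at baseline. There, 10.1 and 5.7.1 can disagree only for symptoms that are not within 14 days of any positive test.

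**Working it through.** **Comparison of the texts**

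| Place | Positive test needed? | 14-day window around |
|---|---|---|
| SAP 10.1, cohort A row (cohort B by reference) | No | The visit with the missing result |
| SAP 5.7.1, cohorts A and B | Yes, local, during the EAP | The positive local test |
| Protocol 11.4.3.1, cohorts A and B | Yes, local | The positive local test |
| Synopsis, cohort A | Yes, local | The positive local test |

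1. The 10.1 row contradicts itself. Its endpoint is RT-qPCR-confirmed infection, and its Estimand cell requires a symptom near a positive RT-qPCR during the EAP. Its Statistical Method cell then supplies a positive result without a test.
2. SAP 6.2 sends the reader to 5.7.1 for missing RT-qPCR rules, for primary and secondary variables.
3. SAP 5.7.3 reuses the 5.7.1 criteria as its first imputation step for the key secondary endpoint of infection regardless of symptoms.
4. SAP 1.2.4 declares no departure from amendment 6, so a symptoms-only rule is not an announced change. All these pointers lead to 5.7.1.

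**Illustration of size**

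Inputs: 1248 seronegative subjects, taken as 624 per arm; attack rates 10% and 5% (SAP 2.2.1); two-sided 0.05 (SAP 5.7.2). The number of false events per arm, k, is an assumption. Neither document gives a source for it.

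Formula: power = Φ{[d − 1.96·√(2·p̄(1−p̄)/n)] / √([p₁(1−p₁)+p₂(1−p₂)]/n)}, where d = p₁ − p₂ and p̄ is their mean. Household clustering is ignored.

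- Plan's figure first, k = 0: p₁ = 0.10, p₂ = 0.05, p̄ = 0.075. Power = Φ[(0.05 − 0.02923)/0.01484] = Φ(1.40) = 0.919. SAP Table 1 gives 0.914 at within-household correlation 0.1, so the formula is close enough for this purpose. Events are 62.4 and 31.2; RR = 0.500.
- k = 5: events are 67.4 and 36.2; RR = 36.2/67.4 = 0.537. p₁ = 0.1080, p₂ = 0.0580, p̄ = 0.0830. Power = Φ[(0.05 − 0.03061)/0.01556] = Φ(1.25) = 0.894.
- Range: k = 1 gives RR 32.2/63.4 = 0.508 and power 0.914. k = 10 gives RR 41.2/72.4 = 0.569 and power 0.867.

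**Does the direction hold if some imputed events are real?**

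Suppose 12.5 imputed events per arm (about 2% of 624), 25 in all.

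- All false: 74.9 and 43.7 events, RR 0.583, power 0.854.
- Half true, split 2:1 placebo to active (8.33 and 4.17), the rest false (6.25 per arm): 62.4 + 8.33 + 6.25 = 76.98 and 31.2 + 4.17 + 6.25 = 41.62 events. RR = 0.541 and power 0.928, slightly above 0.919.

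So the relative risk still moves toward 1, but power need not fall.

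**The case against.** The strongest reply is that this is an editorial slip in a summary cell. The row names a confirmed endpoint, and the full rule appears three times elsewhere. The trial's conduct should also make the affected group small:

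- A swab is to be taken whenever the investigator suspects infection, and evaluation can be by home visit or mobile unit (synopsis, Efficacy Assessment Period; protocol 6.1.4).
- SAP 6.4 maps unscheduled RT-qPCR results to weekly windows, so such a swab can fill a missed visit.
- For hospitalised subjects without a central sample, sites seek local results (protocol 6.1.4).
- Protocol 9.2.2.2 puts symptoms on a separate form when they are tied to a positive RT-qPCR, so a subject never tested may have no symptom record there. This last point is unsettled: SAP 4.5 describes a separate fever form, and SAP 5.8.1 describes the symptom form as self-recorded without that limit.

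This argument on size stands. It does not remove the contradiction, which concerns the event rule of the primary endpoint.

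A second reply also stands in part. No clause formally ranks SAP body text above the appendix, and SAP 6.2 says only where the rules are described. Nor is symptoms-only wording confined to 10.1: SAP 5.7.3 and protocol 11.4.3.2 imply it for the duration endpoints. The case for correcting 10.1 therefore rests on its agreement with nothing else on the primary endpoint, together with the declaration in SAP 1.2.4.

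A reader might infer that the plan leaves two primary analyses open to choice after the data are seen. The documents do not support that, because the protocol, its synopsis, SAP 5.7.1 and the SAP 6.2 pointer all agree. A reader might also infer type I error inflation. Nothing in the documents shows that symptomatic missed swabs would differ by arm, and equal misclassification does not create a difference.

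**Conclusion.** The point holds as a contradiction to be corrected: the imputation sentence in SAP 10.1 is wrong as written, for both cohort rows. It conflicts with SAP 5.7.1, protocol 11.4.3.1, the synopsis, and the endpoint and estimand in its own row.

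The size is unknown and probably small. Dilution of the cohort A effect follows if the added events are false and equal in both arms; loss of power is not established once some of them may be true infections. The illustrative figures rest on an assumed k, the planned rates, 624 per arm and no clustering. They might be read as a ceiling on the harm, but they are not: no bound follows from a count with no source.

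It is worth fixing despite the small expected size, because it concerns what counts as a primary event and the correction is cheap.

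**What to change.** Before unblinding, replace the imputation sentence in SAP 10.1, for both cohort rows, with the 5.7.1 rule. In substance: a subject with COVID-19 symptoms and no central RT-qPCR result during the EAP counts as a symptomatic infection only with a positive local SARS-CoV-2 test and a symptom within 14 days of that test.

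State that this adds to the central-laboratory event definition and does not replace it. For cohort B, state that it also leaves intact the route through the baseline result, under which a subject counts "if subjects have at least 1 symptom within 14 days of a positive RT-qPCR result at baseline or during the EAP".

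Use one version of the limit of the local test to the EAP. It is explicit in SAP 5.7.1 and absent from protocol 11.4.3.1 and the synopsis, so one of the two documents has to be edited.

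As a linked check, reconcile the duration-endpoint wording in SAP 5.7.3 and protocol 11.4.3.2 with 5.7.1. Both exclude visits with a missing RT-qPCR and no nearby broad-term symptom, which by implication lets such a visit count on symptoms alone.

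Cost: one sentence in a SAP appendix table; a short edit to SAP 5.7.1, or to protocol 11.4.3.1 and the synopsis, for the EAP limit; and, if the duration wording changes, a matching edit in both documents. No new data are needed.
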